7. PHARMACOVIGILANCE/ ADVERSE EVENT REPORTING

The Common Terminology Criteria for Adverse Events (CTCAEv4.0) will be used to report adverse events. Please refer to for further details:

https://ctep.cancer.gov/protocolDevelopment/electronic applications/docs/CTCAE v5 Quick Reference 8.5x11.pdf

7.1 Adverse Event (AE)

An AE is any untoward medical occurrence in a patient or clinical trial subject undergoing a trial intervention and which does not necessarily have a causal relationship with this treatment. An AE can therefore be any unfavourable and unintended sign (including an abnormal laboratory finding), symptom, or disease temporally associated with the use of the trial interventions, whether or not considered related to the interventions being evaluated.

i. Adverse Event recording

For the purposes of the study, AEs will be followed up according to local practice until the event has stabilised or resolved, or the Follow-up Visit, whichever is the sooner. All SAEs will be recorded throughout the study and should be reported to the sponsor and any unexpected

Short Title: IP4 - CHRONOS	Protocol No: 19CX5006	Sponsor: Imperial College London	Version: 5.0 Date: 13 th July 2022
			10 daily 2022

and related SAES should also be reported to the REC (as per attached JRCO SOP – appendix 3).

ii. Severity of Adverse Events

Mild: Awareness of event but easily tolerated

Moderate: Discomfort enough to cause some interference with usual activity

Severe: Inability to carry out usual activity

iii. Causality of Adverse Events

Unrelated: No evidence of any causal relationship

- *Unlikely:* There is little evidence to suggest there is a causal relationship (e.g. the event did not occur within a reasonable time after trial interventions). There is another reasonable explanation for the event (e.g. the patient's clinical condition, other concomitant treatment).
- *Possible:* There is some evidence to suggest a causal relationship (e.g. because the event occurs within a reasonable time after administration of the trial interventions). However, the influence of other factors may have contributed to the event (e.g. the patient's clinical condition, other concomitant treatments).
- *Probable:* There is evidence to suggest a causal relationship and the influence of other factors is unlikely.
- *Definite:* There is clear evidence to suggest a causal relationship and other possible contributing factors can be ruled out.

7.2 Abnormal Laboratory Test Results

All clinically important abnormal laboratory test results (apart from PSA) occurring in patients assigned to Arms 2 and 3 in CHRONOS-B will be recorded as adverse events. The clinically important laboratory tests will be repeated at appropriate intervals until they return either to baseline or to a level deemed acceptable by the investigator and the clinical monitor, or until a diagnosis that explains them is made.

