5.10 Laboratory Evaluations

Blood test: PSA will be measured as per standard care and using local laboratory processes and assays. Centralised measure of PSA will not be used. No additional haematology or biochemistry tests will be mandated by the trial. It is envisaged that standard of care haematological and biochemical tests will be ordered by the treating clinician to monitor for pre-assessment requirements for anaesthetic fitness or for assessing treatment related toxicity.

Urinalysis: No additional urinalysis test will be mandated by the trial.

Exploratory / Research samples: Research samples including tissue, blood and urine will be collected and stored as per the details below and will be taken at each of the predefined time points. Protocols for analysis will be added as substantial amendments. Patients will be informed that exploratory studies will take place and consent will be taken for these at initial recruitment. The exact nature of these studies will not be disclosed and further consent in the future will not be asked for prior to proceeding. The following statements have been added to the PIS:

"All samples taken will be transferred to the Imperial College Healthcare Tissue Bank or partner biobank in the UK and will be used for histological, genomic and epigenetic analysis and for ethically approved future studies by our team or other scientists interested in prostate cancer research. Samples will not have any personal information written on them. Researchers will not be able to identify you from your samples."

Short Title: IP4 - CHRONOS	Protocol No: 19CX5006	Sponsor: Imperial College London	Version: 5.0 Date: 13 th July 2022
			10 daily 2022

The following statement has been added to the Informed Consent Form:

"I give permission for any blood, urine and tissue samples, as described in the information sheet, to be used for this and for further ethically approved research in the field of prostate cancer research. I give permission for my samples and data from any scans to be sent and be utilised in research both in the UK and worldwide. All material will be anonymous and I will not be identifiable. I understand that I will not be asked again for permission to run these additional research tests and I may also not be informed of the results."

Sample storage and analysis

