6.6 Drug Interactions/ Precautions/ Contraindications

Finasteride

Interactions:

No drug interactions of clinical importance have been identified.

Precautions:

Obstructive uropathy

Advised for patients to use effective contraception during treatment due to risk of morphological changes in spermatozoa

Contraindications:

Hypersensitivity reaction to 5-alpha reductase inhibitors

Bicalutamide

Interactions:

Severe: none identified Moderate: Lomitapide* Mild: none identified

*theoretical

Precautions:

Risk of photosensitivity- advised to avoid exposure to UV light and sunlight Monitoring of liver function tests required- accumulation may occur in moderate to severe hepatic impairment

Protocol No: 19CX5006 v5.0 13th July 2022

Short Title: IP4 - CHRONOS	Protocol No: 19CX5006	Sponsor: Imperial College London	Version: 5.0 Date: 13 th July 2022
			13 July 2022

Advised for patients to use effective contraception during treatment due to risk of morphological changes in spermatozoa

No dose adjustment is required in the elderly patients or patients with renal impairment

Contraindications:

Hypersensitivity to anti-androgen therapy

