11.4 Early Discontinuation of the Study

In case of early discontinuation of the study, the Follow-up Visit assessments should be performed for each subject, as far as possible.

The following reasons may result in early discontinuation:

- Early evidence that a treatment arm is harmful. If only one treatment arm is deemed to be harmful then the remaining arms of the study may continue as planned, OR
- It is not feasible to reach the planned outcomes (A hazard ratio of 0.7 to 1 will make the intervention not worth progressing with given the severe adverse effects associated with it)

The statistical criteria for termination of the study will be detailed in the statistical analysis plan (SAP). At the end of the study patients undergoing focal therapy will continue to be followed up locally within their recruitment centres within the ICE (European Registry for Cryosurgical Ablation of the prostate, EuCAP) or the HEAT international HIFU registry as per NICE guidelines IPG432/IPG42.

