8.2. Safety Variables

An adverse event (AE) is any untoward medical occurrence in a patient or clinical trial subject undergoing a trial intervention and which does not necessarily have a causal relationship with this treatment. An AE can therefore be any unfavourable and unintended sign (including an abnormal laboratory finding), symptom, or disease temporally associated with the use of the trial interventions, whether or not considered related to the interventions being evaluated.

A serious adverse event (SAE) is defined as any event that:

- Results in death;
- Is life-threatening*;
- Requires hospitalisation or prolongation of existing inpatient's hospitalisation**;
- Results in persistent or significant disability or incapacity;
- Is a congenital abnormality or birth defect.
- * "Life-threatening" in the definition of "serious" refers to an event in which the subject was at risk of death at the time of the event; it does not refer to an event which hypothetically might have caused death if it were more severe.
- ** "Hospitalisation" means any unexpected admission to a hospital department. It does not usually apply to scheduled admission that were planned before study inclusion or visits to casualty (without admission).

AE reporting will utilise NCI CTCAE v4.0 terminology, providing a grading (severity) scale for each AE term. The expected adverse events that may require hospitalisation and serious adverse events that will not require reporting as SAEs, but that will be collected, are listed in **Error!**Reference source not found.

All protocol deviations and violations will be recorded throughout the study and reported.

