----------------------------------	--	---------

Table 2. 17: Listing of all Adverse Events*

Treatment group	Subject ID	Site	AE Number	AE Term	Onset Date	End Date	Ongoing	Severity	Severity Grade	Relationship to Study IMP	Action Taken Concerning Study IMP	Outcome	Serious?

^{*}Report adverse events for CHRONOS-A and CHRONOS-B separately

Table 2. 18: Summary of Adverse Events² by Severity Grade (v4.0 CTCAE), by Treatment Arm*

	Subjects with AEs ¹					
Treatment	1	2	3	4	5	Total
	xxx (xx%)	xxx (xx%)	xxx (xx%)	xxx (xx%)	xxx (xx%)	xxx (xx%)
	xxx (xx%)	xxx (xx%)	xxx (xx%)	xxx (xx%)	xxx (xx%)	xxx (xx%)
	xxx (xx%)	xxx (xx%)	xxx (xx%)	xxx (xx%)	xxx (xx%)	xxx (xx%)
Total	xxx (xx%)	xxx (xx%)	xxx (xx%)	xxx (xx%)	xxx (xx%)	xxx (xx%)

	All AEs					
Treatment	1	2	3	4	5	Total
	xxx (xx%)					
	xxx (xx%)					
	xxx (xx%)					
Total	xxx (xx%)					

^{*}Report adverse events for CHRONOS-A and CHRONOS-B separately

¹Where subjects have more than one AE, the highest severity grade has been used

²Expected adverse events which will not be reported are listed in Appendix 1

Imperial Clinical Trials Unit	STATISTICAL ANALYSIS PLAN: FEASIBILITY	CHRONOS
----------------------------------	--	---------

Table 2. 19: Number of Adverse Events² by Relationship to study treatment, by Treatment Arm*

	Subjects with AEs	s ¹					
Treatment	Definitely	Probably	Possibly	Unlikely	Not related	Not assessable	Total
	xxx (xx%)	xxx (xx%)	xxx (xx%)	xxx (xx%)	xxx (xx%)	xxx (xx%)	xxx (xx%)
	xxx (xx%)	xxx (xx%)	xxx (xx%)	xxx (xx%)	xxx (xx%)	xxx (xx%)	xxx (xx%)
	xxx (xx%)	xxx (xx%)	xxx (xx%)	xxx (xx%)	xxx (xx%)	xxx (xx%)	xxx (xx%)
Total	xxx (xx%)	xxx (xx%)	xxx (xx%)	xxx (xx%)	xxx (xx%)	xxx (xx%)	xxx (xx%)

	All AEs						
Treatment	Definitely	Probably	Possibly	Unlikely	Not related	Not assessable	Total
	xxx (xx%)	xxx (xx%)	xxx (xx%)	xxx (xx%)	xxx (xx%)	xxx (xx%)	xxx (xx%)
	xxx (xx%)	xxx (xx%)	xxx (xx%)	xxx (xx%)	xxx (xx%)	xxx (xx%)	xxx (xx%)
	xxx (xx%)	xxx (xx%)	xxx (xx%)	xxx (xx%)	xxx (xx%)	xxx (xx%)	xxx (xx%)
All subjects	xxx (xx%)	xxx (xx%)	xxx (xx%)	xxx (xx%)	xxx (xx%)	xxx (xx%)	xxx (xx%)

^{*}Report adverse events for CHRONOS-A and CHRONOS-B separately

Table 2. 20: Listing of all Serious Adverse Events by Category*

Treatment group	Subject ID	Site	SAE number	SAE term	SAE Description	Date of notification	Why was the event serious?	Date of onset	Severity	Outcome	Date of outcome	Causal relationship to event	Expectedness	Action taken

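### Protocol 7.2 makes recording of abnormal laboratory results as adverse events mandatory in the two CHRONOS-B drug arms and is silent on the focal-alone control, so laboratory AEs are not collected on equal terms

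*Protocol*

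**What the plan says.** Protocol 7.1 defines an AE for any participant undergoing a trial intervention, as "any unfavourable and unintended sign (including an abnormal laboratory finding), symptom, or disease temporally associated with the use of the trial interventions". SAP 8.2 repeats that definition without restriction by arm. Protocol 7.2 then adds a specific instruction: clinically important abnormal results other than PSA "occurring in patients assigned to Arms 2 and 3 in CHRONOS-B will be recorded as adverse events". Arm 1 of CHRONOS-B is not mentioned, either to include or to exclude it.

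On testing, Protocol 5.10 states: "No additional haematology or biochemistry tests will be mandated by the trial". It continues: "It is envisaged that standard of care haematological and biochemical tests will be ordered by the treating clinician", for anaesthetic fitness or for treatment toxicity. Protocol 6.6 lists under bicalutamide: "Monitoring of liver function tests required".

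On analysis, Protocol 8.3 looks at AE occurrence in each arm. SAP 9.3 lists and summarises AEs by arm, separately for CHRONOS-A and CHRONOS-B. Table 2.18 does so "by Severity Grade (v4.0 CTCAE), by Treatment Arm", and Table 2.19 by relationship to treatment. SAP 8.3 and the footnotes to both tables leave out the expected events in Appendix 1.

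**The concern.** A by-arm AE table can be read as a comparison only if the same event has the same chance of being written down in each arm. Here the text gives sites an obligation for Arms 2 and 3 and, for Arm 1, only a definition under which the finding may count. Staff know the allocation and so know which instruction applies. Control men can also have routine bloods, for instance before an anaesthetic, so there are results in that arm that could go unrecorded.

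AE rates and complications are a main-study secondary endpoint (Protocol 2.6), and pilot participants carry forward into the main stage (Protocol 8.1.1), so unequal records would persist. AE data may also inform decisions about an arm. Protocol 1.2.1 speaks of stopping arms whose adverse event rate is too high, and Protocol 11.4 lists "Early evidence that a treatment arm is harmful" among the reasons for early discontinuation. Protocol 11.4 refers to the SAP for statistical stopping criteria, but SAP Section 11 gives only a recruitment threshold. With no harm threshold set, the committee would have to judge from tables such as these.

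**Working it through.** **Comparing the texts.** Protocol 7.1 and SAP 8.2 say what an AE can be, in every arm. Protocol 7.2 says what will be recorded, in two named arms. The two are compatible, and together they leave recording required in Arms 2 and 3 and open in Arm 1. CHRONOS-A is not named in 7.2 either, but neither of its arms is, and it is summarised separately, so no between-arm imbalance arises there from this rule.

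**Illustrating the size.** The documents give no AE rate and no laboratory-abnormality rate, so there is no planned figure to reproduce. The following inputs are assumptions:

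- q, the risk of a clinically important laboratory abnormality: 5%, 10% or 20%, the same in every arm
- b, the risk of any other tabulated AE: 20% or 40%, the same in every arm and independent of q
- c, the share of control-arm laboratory abnormalities that are recorded: 0, 50% or 100% (drug arms: all recorded)

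The arm sizes are from Protocol 3.2: 20 per arm in the pilot and 400 per arm in the main stage.

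Probability that a man has at least one recorded AE:

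- drug arm: 1 − (1 − b)(1 − q)
- control: 1 − (1 − b)(1 − cq)
- spurious excess: (1 − b) × q × (1 − c)

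For example, with b = 20%, q = 10% and c = 0, the drug arm is 1 − 0.80 × 0.90 = 28%, control is 20%, and the excess is 8 points.

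| b | q | Drug arm | Control, c = 0 | Excess, c = 0 | Excess, c = 50% | Excess, c = 100% |
|---|---|---|---|---|---|---|
| 20% | 5% | 24% | 20% | 4 | 2 | 0 |
| 20% | 10% | 28% | 20% | 8 | 4 | 0 |
| 20% | 20% | 36% | 20% | 16 | 8 | 0 |
| 40% | 5% | 43% | 40% | 3 | 1.5 | 0 |
| 40% | 10% | 46% | 40% | 6 | 3 | 0 |
| 40% | 20% | 52% | 40% | 12 | 6 | 0 |

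Excesses are in percentage points. In men per arm (n × excess):

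- c = 0: 0.03 × 20 = 0.6 to 0.16 × 20 = 3.2 in the pilot; 0.03 × 400 = 12 to 0.16 × 400 = 64 in the main stage
- c = 50%: 0.3 to 1.6 in the pilot; 6 to 32 in the main stage
- c = 100%: none

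For any given q and b, the result turns on c, and c is what Protocol 7.2 leaves open.

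**The case against.** The strongest reply is that 7.2 excludes nobody. The general definition already covers a control-arm laboratory finding, and the visit schedule (Protocol 5.7) has AE review from visit 2 onwards without restriction by arm. Arms 2 and 3 are the only arms with an investigational drug, so an explicit reminder there is ordinary pharmacovigilance. This stands to the extent that the documents do not tell sites to ignore control results. It does not settle the matter: a definition of what may be an AE is weaker than an instruction to record, and if the definition already secured full recording everywhere, naming two arms in 7.2 would add nothing.

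A second reply is that nothing formal depends on the tables. This is correct. The SAP covers the feasibility stage, its AE tables carry no between-arm test, the safety analysis in both documents is a tabulation of SAEs (Protocol 8.3, SAP 9.8), and the numerical progression criteria concern recruitment and compliance. Table 2.17 lists each AE by term, so laboratory AEs could be picked out, and results judged unrelated would appear as such in Table 2.19. Table 2.18, however, does not separate by relatedness or by laboratory origin.

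A third reply is that the Appendix 1 exclusion works the other way. It removes expected systemic-therapy toxicity, including breast tenderness, decreased libido and neutropenia, which would fall mainly in the drug arms. This also stands, and it prevents any claim about the net direction. It does not restore a fair comparison of laboratory AEs, since most of the excluded items are symptoms and liver function abnormalities are not among them.

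**Conclusion.** The recording rule for laboratory AEs is unequal between the CHRONOS-B drug arms and their control, and the by-arm summaries make no allowance for it. Considered alone, any under-recording in control inflates the drug arms' relative count. The illustrated excess runs from 0 to 16 points and depends on assumed risks and on an unknown share of control results recorded. The importance is minor to moderate.

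A reader might go further and infer that laboratory abnormalities are AEs only in the drug arms, so that the comparison counts against the drugs by construction, with 20 to 80 of 400 drug-arm men against none in control (5-20% of 400). The documents do not support that. Zero recording in control is the extreme case and is not prescribed, men with another AE are already counted once at subject level, and the Appendix 1 exclusion pulls the other way. Nor do the documents show that such a difference would trigger stopping for harm, because no AE threshold is stated.

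**What to change.** Reword Protocol 7.2 so that the same recording rule applies to patients in every arm of CHRONOS-B, and carry this into the CRF guidance. If the restriction is kept for pharmacovigilance, flag the records made under 7.2 and tabulate them separately from the between-arm counts in SAP Tables 2.18 and 2.19.

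In either case, show laboratory AEs with the number of men tested in each arm. A common recording rule does not equalise how often men are tested, and the mention of liver function monitoring for bicalutamide alone suggests that testing may differ. Protocol 5.10 and 6.6 should also be reconciled on whether any such tests are required by the trial; which of the two is right is not a matter for this review.

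The cost is one sentence in the protocol, a line in the CRF guidance, an added row or footnote in the SAP tables, and a few more AE forms in the control arm from blood tests already being done. No new tests are needed.

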7.3 Serious Adverse Events (SAE)

i. Definition of SAE

An SAE is defined as any event that:

- Results in death;
- Is life-threatening*;
- Requires hospitalisation or prolongation of existing inpatient hospitalisation**;
- Results in persistent or significant disability or incapacity;
- Is a congenital abnormality or birth defect;

^{* &}quot;Life-threatening" in the definition of "serious" refers to an event in which the subject was at risk of death at the time of the event; it does not refer to an event which hypothetically might have caused death if it were more severe.

Short Title: IP4 - CHRONOS	Protocol No: 19CX5006	Sponsor: Imperial College London	Version: 5.0 Date: 13 th July 2022
			10 daily 2022

** "Hospitalisation" means any unexpected admission to a hospital department. It does not usually apply to scheduled admissions that were planned before study inclusion or visits to casualty (without admission).

Medical judgement should be exercised in deciding whether an adverse event/reaction is serious in other situations. Important adverse events/reactions that are not immediately life-threatening, or do not result in death or hospitalisation but may jeopardise a subject, or may require intervention to prevent one of the other outcomes listed in the definition above should also be considered serious.

List of expected adverse events that may require hospitalisation and serious adverse events that will not require reporting as SAEs but will be collected:

- Urinary retention and any admission required for this
- Urinary tract infection and any admission required for this
- Epididymo-orchitis and any admission required for this
- Dysuria
- Debris in urine and any admission required for this
- Haematuria and any admission required for this
- Erectile dysfunction and any other sexual sequelae side-effects such as dry orgasm, lack of orgasm, poor libido
- Urinary incontinence
- Rectal discomfort, bleeding, diarrhoea
- Recto-urethral fistula and any operations required for this
- Lethargy, tiredness, poor appetite
- Urethral stricture and any operations required for this
- Transurethral resection of prostate and any operations required for this
- Operations required for symptoms of bladder outlet obstruction
- Any expected complication related to post-operative course from radical prostatectomy i.e. lymphocoele, bowel injury, haematoma needing percutaneous drainage
- Expected toxicity from systemic therapy such as neutropenia, neutropenic sepsis, weight gain, decreased libido, breast tenderness, metabolic syndrome, lethargy, fatigue, osteoporosis, nausea and vomiting, diarrhoea, constipation, muscle/joint pains and hair loss.
- Bowel stricture post radiotherapy, and procedures required for this

ii. Reporting of SAEs

Rapid reporting of all SAEs i.e. within 24 hours, occurring during the study must be performed as detailed in SAE reporting instructions. If the investigator becomes aware of safety information that appears to be intervention related, involving a subject who participated in the study, even after an individual subject has completed the study, this should be reported to the Sponsor.

All SAEs will be reviewed by the Chief Investigator or a designated medically qualified representative to confirm expectedness and causality.

Reporting of SAEs and review by the CI will be via the trial data collection system (CRF/electronic case report form [InForm]).

iii. Related SAEs

Related: results from administration of any research procedures

Short Title: IP4 - CHRONOS	Protocol No: 19CX5006	Sponsor: Imperial College London	Version: 5.0 Date: 13 th July 2022
			10 daily 2022

iv. Unexpected SAEs

Unexpected: type of event is not listed in the protocol as an expected occurrence

v. Reporting of SAEs that are related and unexpected

Please Note: These reporting requirements refer to CHRONOS-A only

An SAE form should be completed on the InForm eCRF within 24 hours. However, relapse, death and/or hospitalisations for elective treatment of a pre-existing condition do not need reporting as SAEs.

All related and unexpected SAEs should be reported to the relevant REC as per the following definition. In the opinion of the Chief Investigator, the event was:

- 'Related', i.e. resulted from the administration of any of the research procedures; and
- 'Unexpected', i.e. an event that is not listed in the protocol as an expected occurrence Reports of related and unexpected SAEs should be submitted within 15 days of the Chief Investigator becoming aware of the event, using the *NRES SAE form for non-IMP studies*. The Chief Investigator must also notify the Sponsor of all SAEs. Local investigators should report any SAEs as required by their Local Research Ethics Committee, Sponsor and/or Research & Development Office.

Contact details of sponsor for reporting SAEs are as follows:

Joint Research Compliance Office:

Imperial College London and Imperial College Healthcare NHS Trust

E-mail: [contact]

Chief Investigator:

[name] [name]

Imperial College London, Charing Cross Campus

E-mail: [contact] and [contact]

[contact] (Mon to Fri 09.00 –17.00)

vi. Definition of a Serious Adverse Reaction (SAR)

Please Note: This definition refers to CHRONOS-B only

A SAR is defined as a SAE that is judged to be related to any dose of study drug administered to the subject.

For the purpose of this study, reactions would apply to the combined administration of neoadjuvant therapies with focal therapy:

- Neoadjuvant finasteride followed by focal therapy
- Neoadjuvant bicalutamide followed by focal therapy

vii. Definition of Suspected Unexpected Serious Adverse Reaction (SUSAR)

Please Note: This definition refers to CHRONOS-B only

Short Title: IP4 - CHRONOS	Protocol No: 19CX5006	Sponsor: Imperial College London	Version: 5.0 Date: 13 th July 2022
			10 daily 2022

Any SAR that is NOT consistent with the applicable product information as set out in the Summary of Product Characteristics (SmPC).

viii. Reporting of SUSARS

Please Note: These reporting requirements refer to CHRONOS-B only

SUSARS should be notified to the appropriate regulatory authority, the relevant REC and the Sponsor in accordance with regulatory requirements. SUSARs which are fatal or life-threatening will be reported no later than seven days after alerting the Sponsor to the reaction. Any additional relevant information will be sent within eight days of the report. A SUSAR which is not fatal or life-threatening will be reported within 15 days. Follow-up of patients who have experienced a SUSAR should continue until recovery is complete or the condition has stabilised.

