1.4 Risk/Benefit Assessment

CHRONOS-A

Risks: Some centres may not be equipped with facilities to provide FT or radical therapy, and therefore patients may need to travel to another hospital site. This is what currently happens in clinical practice. Side effects associated with focal therapy include incomplete treatment of the index lesion, and anxiety related to this. Further, it is expected that 1 in 5 patients that undergo focal treatment will require a repeated procedure within 5 years of treatment. Risks associated with radical treatment include urinary incontinence, erectile dysfunction, bowel problems, significant bleeding, urethral stricture, bowel strictures and side-effects from hormonal therapy such as loss of libido, hot flushes and breast tenderness. Men who undergo radical radiotherapy may require pre-procedure intervention to manage pre-existing lower urinary tract symptoms.

Protocol No: 19CX5006 v5.0 13th July 2022

Short Title: IP4 - CHRONOS	Protocol No: 19CX5006	Sponsor: Imperial College London	Version: 5.0 Date: 13 th July 2022
			10 daily 2022

Benefits: Men undergoing focal therapy can expect a lower likelihood of developing urinary incontinence, erectile dysfunction, bowel problems and shorter post-treatment recovery time relative to those undergoing radical treatment. Those undergoing radical treatment should have less anxiety regarding incomplete treatment of their cancer and follow up for disease relapse is likely less burdensome to healthcare provider and patient.

CHRONOS-B

Risks: Men randomised to the focal therapy and neoadjuvant treatment arm may experience side effects from the neoadjuvant therapy, which can include weight gain, decreased libido, breast tenderness, gynaecomastia and hair loss.

Benefits: The time in which men require repeat focal therapy, or salvage/ whole gland therapy is hypothesised to increase with the use of neo-adjuvant treatments, with fewer significant side effects as observed in the radical therapy treatment arm.

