6. TREATMENTS

6.1 Investigational Medicinal Product (IMP) Details

Neoadjuvant finasteride and bicalutamide are used within standard practice. However, they are considered investigational medicinal products within CHRONOS as they are being used to discover, verify and compare their clinical effects with focal therapy.

CHRONOS-B (only)

- Arm 2 (Intervention arm): **Neoadjuvant finasteride** 5mg once daily for a minimum of 12 weeks (84 days) followed by focal therapy.
- Arm 3 (Intervention arm): **Neoadjuvant bicalutamide** 50mg once daily therapy for a minimum of 12 weeks (84 days) followed by focal therapy.

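### The list of serious events exempt from SAE reporting has no arm limit and contradicts the duty to report all SAEs, so a CHRONOS-B study-drug reaction can miss the SmPC check

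*Protocol*

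**What the plan says.** Protocol 7.3 i defines an SAE by the usual seriousness criteria. It then lists events described as "serious adverse events that will not require reporting as SAEs but will be collected". One item reads "Expected toxicity from systemic therapy such as neutropenia, neutropenic sepsis, weight gain, decreased libido, breast tenderness, metabolic syndrome" and goes on to further effects, osteoporosis among them. Other items cover urinary retention, infection and haematuria with any admission they need. SAP Appendix 1 repeats the list. Neither version restricts it to a trial or an arm.

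Two sections say something different. Protocol 7.1 i has all SAEs recorded throughout and reported to the sponsor. Protocol 7.3 ii asks for rapid reporting, within 24 hours, of all SAEs. It also says: "All SAEs will be reviewed by the Chief Investigator or a designated medically qualified representative to confirm expectedness and causality".

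Finasteride and bicalutamide count as study drugs: "they are considered investigational medicinal products within CHRONOS" (Protocol 6.1). For CHRONOS-B, 7.3 vi defines a SAR as an SAE judged related to study drug, and 7.3 vii defines a SUSAR as "Any SAR that is NOT consistent with the applicable product information as set out in the" SmPC. Section 7.3 iv, with no trial restriction, instead treats an event as unexpected when the protocol's own list does not contain it. Section 7.3 v, which gives the 15-day ethics committee route, opens with "Please Note: These reporting requirements refer to CHRONOS-A only" and says death need not be reported as an SAE.

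**The concern.** In a trial with investigational drugs, a serious event should be judged for relatedness and compared with the SmPC before anyone decides that it needs no expedited report. Here the list can act first. A serious event named on it may be recorded only as a collected event, and the written procedure then gives nobody the task of asking whether the drug caused it or whether the SmPC covers it. If the event were related and outside the SmPC, it would meet the SUSAR definition, but the list would have kept it out of the review that starts the 7-day or 15-day clock.

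The list also names serious events that the protocol does not itself attribute to these drugs. Its risk statement for the CHRONOS-B drug arms (1.4) speaks of side effects "which can include weight gain, decreased libido, breast tenderness, gynaecomastia and hair loss". Neutropenia, neutropenic sepsis, metabolic syndrome and osteoporosis are not among them.

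**Working it through.** No power or sample-size arithmetic applies. The check is to follow one event through the text and set the conflicting sections side by side.

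**Does the list reach the drug arms?** Yes, as written.
- Sections 7.3 v to viii each carry a note limiting them to CHRONOS-A or CHRONOS-B, but the list carries none.
- Four of the five side effects that 1.4 names for the CHRONOS-B drug arms (weight gain, decreased libido, breast tenderness, hair loss) are in the same systemic-therapy item. Only gynaecomastia is not. A site would naturally apply the item to finasteride and bicalutamide.

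**Trace of one event.** Suppose a man on a study drug is admitted with neutropenic sepsis.
1. The unplanned admission meets the seriousness criteria in 7.3 i.
2. The event is on the list, so 7.3 i says it need not be reported as an SAE. Sections 7.1 i and 7.3 ii say all SAEs are reported. Nothing states which prevails.
3. If the site follows the list, there is no SAE report. Review of causality and expectedness under 7.3 ii, which runs through the SAE reporting system, has nothing to act on.
4. The SAR definition (7.3 vi) needs an SAE judged related to drug, and the SUSAR definition (7.3 vii) needs a SAR. On paper the event still fits both. In practice no step makes either judgement for a collected-only event.
5. If someone does ask whether the event is expected, 7.3 iv points to the protocol list (expected) and 7.3 vii to the SmPC (not shown). The two can give opposite answers.

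**What the analysis would recover.**
- SAP 8.3 confines its adverse-event variable to events outside Appendix 1.
- Footnotes to SAP Tables 2.18 and 2.19 say the listed expected events will not be reported.
- SAP 9.8 tabulates serious adverse events, so a listed event never entered as an SAE would not be counted there.
- SAP Table 2.17, a listing of all adverse events, carries no such footnote and has columns for seriousness and relationship to the study drug. A listed event may appear there.

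**Men exposed** (Protocol 3.2). Pilot: 20 + 20 = 40 on study drug. Main stage: 400 + 400 = 800. The focal-only CHRONOS-B arm has 20 and 400. The Trial Summary and 8.1.1 give 1260 rather than 1200 for CHRONOS-B. With equal allocation that is 1260 / 3 = 420 per arm, or 840 on study drug.

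**The case against.** The strongest reply is that the protocol already requires these events to be reported. Sections 7.1 i and 7.3 ii cover all SAEs, and 7.3 ii adds a duty to tell the sponsor of safety information that appears related to the intervention. A SAR is defined as a related SAE, not as a related SAE that was reported, so 7.3 viii still applies to a listed event. Section 7.2 records clinically important laboratory abnormalities in Arms 2 and 3 as adverse events, and 7.1 iii supplies causality grades for adverse events. The word expected in the systemic-therapy item might also be read as excluding anything not expected of the particular drug.

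Much of this stands. It rules out the reading that sites following the protocol exactly would necessarily leave a reaction unreported: the text contradicts itself, and a site could report under the general duties. It does not remove the problem. None of those duties says it overrides the specific exemption, none includes an SmPC comparison for a listed event, and the item names neutropenic sepsis outright without pointing to the SmPC.

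A reader might also infer four further things that the documents do not support.
- That the study drugs are the only systemic therapy in CHRONOS-B, so the item must belong to CHRONOS-A. Salvage systemic therapy is part of the CHRONOS-B endpoint (2.5) and is collected as a secondary outcome (2.6). The item's intended scope is not stated.
- That focal-only CHRONOS-B men have no ethics committee route. Section 7.1 i sends unexpected and related SAEs to the committee under an attached SOP with no CHRONOS-A limit. That SOP is not shown and may hold the timelines.
- That the committee's judgement of harm (11.4) rests on the SAE tables by category. No section says so.
- That a SUSAR has been or will be missed. The SmPCs are not in the documents, so whether either drug's SmPC lists these events cannot be checked.

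**Conclusion.** The point holds as a contradiction in the reporting rules and a missing step. The 7.3 i list exempts named serious events in every arm, 7.1 i and 7.3 ii require all SAEs to be reported, and no sentence has a collected-only event compared with the SmPC. Section 7.3 iv adds a rival standard of expectedness. A reaction to finasteride or bicalutamide can therefore be missed. The text does not show that it will be, because the data are still collected and the general duties remain.

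The figures of 40 pilot and 800 main-stage men describe exposure to the ambiguous rule, not a count of lost reports, and the main stage depends on funding. The conclusion assumes that the SOP and SAE instructions outside these documents do not already resolve the conflict. If they do, the protocol should say so.

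**What to change.** 1. Reconcile Protocol 7.1 i, 7.3 i and 7.3 ii. State that any listed event meeting the seriousness criteria in a man who has received a CHRONOS-B study drug is assessed for relatedness to that drug and against the SmPC before any exemption applies. The SUSAR timelines run if it is related and not consistent with the SmPC.
2. Limit 7.3 iv to CHRONOS-A or to events not involving a study drug, so that the SmPC is the only expectedness reference for study-drug reactions.
3. In the SAP, align Appendix 1, the 8.3 variable and the footnotes to Tables 2.18 and 2.19 with this. Tabulate listed serious events in the same way in all arms of each trial.
4. Reconcile 7.3 v, where death is not reportable as an SAE in CHRONOS-A, with 7.1 i. State which route and timeline cover related and unexpected SAEs in CHRONOS-B men who receive focal therapy alone.

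A simpler change, lifting the exemption for Arms 2 and 3 only, should be avoided. The same admission for retention or infection after ablation would then count as an SAE in the drug arms but not in the control arm, which would distort the comparison. Step 3 prevents this.

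The cost is a protocol amendment and matching SAP edits, plus extra causality and expectedness assessments for listed admissions in the drug arms. The documents do not allow that number to be estimated. The events are already collected, and the design does not change.
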